30 to classical methods. In SIRIUS we will prospectively challenge this hypothesis to address the
31 question of how often a better or final diagnosis can be delivered by WGS and/or WTS and if
32 unclear cases can be efficiently resolved.

33

34 **Type of Research:** observational study, diagnostic study, hematology, leukemia, next
35 generation sequencing

36

37 **Intervention:** none

38 **APPROVAL**

39 This study will be conducted with the utmost respect for individual patients in accordance with
40 the requirements of this diagnostic trial protocol and especially in accordance with the
41 following:

42 • Good clinical practice directive (European Union) (2005/28/EC)

43 • The ethical principles in accordance with the Declaration of Helsinki

44 • International Conference on Harmonization (ICH) E6 Good Clinical Practice:
45 consolidated guideline

46 • Guidelines for Good Clinical Practice (*Deutsche Forschungsgemeinschaft DFG*)

47 • Standards and guidelines for the interpretation of sequence variants (PMID: 25741868)

48 • All applicable laws and regulations, including, without limitation, data privacy laws,
49 clinical trial disclosure laws, and regulations.

50 **I. INTRODUCTION**

51 1. Background and Rationale

52 Treatment of hematological diseases relies on a single cardinal prerequisite: correct
53 classification within the broad specter of malignant diseases arising from the hematopoietic
54 system. With the ever-expanding availability of distinct yet complementary diagnostic tools,
55 our understanding of the landscape of hematological diseases steadily increases. As such, the
56 current consensus classification as summarized through the WHO classification (2017)
57 represents a compass guiding diagnostic algorithms to the correct diagnosis. Today, the gold
58 standard of routine diagnostic process relies on five methodological pillars: cytomorphology,
59 histology, chromosomal cytogenetics, immunophenotyping, and molecular genetic testing.
60 This leads to a treatment enabling diagnosis in the vast majority of cases. However,
61 approximately 10 % of cases remain unresolved from a diagnostic point of view and hence do
62 not lead to a satisfactory diagnosis according to current WHO standards (2017). We intend to
63 solve this issue to provide illuminating diagnostic guidance for the best possible patient's care.

64 2. Objectives

65 To address this problem, we hypothesize that novel high throughput sequencing methods, e.g.,

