66 whole genome and/or whole transcriptome sequencing are able – by virtue of painting a more
67 delicate genetic portrait of a tumor sample – to provide a more accurate diagnosis.
68 To this end we generated a reference collection of 5,500 samples with the full spectrum of
69 hematological malignancies, for which we performed whole-genome sequencing as well as
70 whole-transcriptome sequencing. Moreover, gold standard diagnoses according to WHO
71 classification with all needed techniques, all performed in MLL, clinical data and therapy
72 response data are fully available for these cases. The main advantage of this reference

73 collection consists of the unambiguity of each diagnosis, providing a reference framework for
74 any further classification and diagnosis especially in difficult cases.

75 Therefore, SIRIUS will compare the diagnostic superiority of WGS or WTS to the combined
76 approach with gold standard results and by matching the obtained results to the nearest “digital
77 sibling” within our reference cohort of more than 5,500 WGS and WTS (both in 93% of cases).

78 To this end, we will use an inhouse developed matching algorithm, which is able to match
79 genomic or transcriptomic profiles to a group of similar cases and gold standard results from
80 timepoint of this study. Current workflows intended to generate WTS/WGS data from patient
81 samples – all while fulfilling state of the art accreditation (ISO 15189) – require up to 5 – 7
82 days. This is largely comparable to classical methods but holds the promise to replace error
83 prone and arduous iterations in the methodological work up. The objective is to test whether
84 WTS and/or WGS based approaches can surpass classical methods regarding diagnostic
85 precision and routine reliability. Here we will test this hypothesis in a prospective real-world
86 setting under diagnostically difficult circumstances.

87 **II. STUDY DESIGN**

88 1. Type of Study

89 SIRIUS is conducted as a monocentric prospective case-control study. The study population
90 consists of carefully chosen patients with potential hematological malignancy, for which
91 current diagnostic methods were not sufficient to provide clear-cut diagnosis and definitive
92 clinical guidance. SIRIUS is entirely a non-interventional study without therapeutic
93 consequences for direct patient care. Data will be used as research study and micro-cost
94 analysis will be provided.

95 2. Duration of Study

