96 SIRIUS will be conducted for a total number of 110 patients with inconclusive diagnosis by
97 gold standard techniques for a total of up to nine months after the first enrollment. Patients to
98 qualify for study will be selected by referring center and PI before material is send to MLL.

99 3. Quality Control

100 Due to the heterogeneity in quality of blood and bone marrow samples arriving at MLL,
101 SIRIUS is preceded by a rigorous quality assessment of every patient history, data already
102 available and sample source and quality to be potentially included in the present study. The
103 minimal requirements are listed in III.

104 4. Primary Study Endpoints

105 Overall, the efficacy and supremacy of WGS/WTS analysis will be subjected to current
106 standard procedures. The primary endpoint will be assessed as follows: unclear cases will be
107 subjected to three diagnostic algorithms:

108 (1) Inhouse at referring site by histopathological diagnosis in the context of a hematological
109 tumor board according to current standards (“best practice”)

110 (2) Current gold-standard diagnostic workup as performed routinely by the MLL,
111 consisting of

112 a. Cytomorphological diagnosis
113 b. Immunophenotypic diagnosis
114 c. Chromosomal banding analysis
115 d. Molecular testing
116 e. NGS based Targeted panel sequencing

117 (3) WGS and WTS sequencing plus matching to nearest digital sibling in 5,5k cohort

118 The results of (2) and (3) arms will be first compared to the result obtained in (1) since this is
119 the therapy guiding approach *in domo*. Clinical follow-up observations will be made to assess
120 the success of this first diagnosis.

121 Next results from (2) and (3) will be compared against each other to obtain an assessment of
122 replaceability of current gold-standard methods to either WGS or WTS and WGS/WTS
123 combined. If both approaches do not yield a similar conclusion, specific data from (2) will be
124 added to results in (3) until a definitive assessment can be made.

125 5. Secondary Study Endpoints

126 • Turn-over time until potential therapy guiding diagnosis
127 • Cost-effectiveness until timepoint of diagnosis and therapy
128 • Compare WES to WGS data in SIRIUS cohort
129 • Identify number of potential actionable targets for which a therapy has been approved
130 but identification was missed in (1) and (2)
131 • Identify putative disease stage in comparison to (2) and clinical history

132

133

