134 **III. SUBJECT SELECTION AND WITHDRAWAL**

135

136 1. Number Of Subjects

137 SIRIUS intends to enroll a total number of 110 cases provided by approximately 50 certified
138 hematological centers.

139

140 2. Gender, Age

141 Patients' samples from both sexes will be used (male and female). Only samples from adult
142 patients (18 years or older) will be used.

143

144 3. Inclusion Criteria

- 145 • Patients having been investigated with a suspected hematological disorder and:
 - 146 ○ Having unclear diagnosis after internal routine diagnosis
 - 147 ○ Unusual clinical course
 - 148 ○ Unusual r/r status or non-responder
 - 149 ○ Multiple parallel hematological conditions
 - 150 ○ Difficult/rare therapy associated/secondary neoplasms
- 151 • Current diagnostic work-up is not satisfactory in terms of (1) accuracy (2) clinical
152 behavior
- 153 • Only samples of patients min. 18 years of age will be used
- 154 • Material with a minimum of 20% tumor content in bone-marrow or peripheral blood
155 sample
- 156 • Samples must suffice quality attributes control which are denoted in (4.)
- 157 • Patient's informed consent

158 4. Exclusion Criteria

159 • Sample is not fit for state-of-the-art diagnosis, fails initial quality control. For quality
160 insurance we will exclude samples with wrong anticoagulant sent. Samples with
161 damage due to meteorological reasons (freeze-thaw damage or elevated temperature)
162 will be excluded.

163 • Samples with too scarce material jeopardizing routine gold-standard diagnosis will be
164 excluded (tumor content < 20 %).

165

166 5. Location

167 SIRIUS will be conducted as monocentric trial at the MLL.

168 **IV. STATISTICAL PLAN**

169

170 To determine the statistical significance within the endpoint analysis we will assess both
171 quantitative as well as qualitative variables. Quantitative variables will be described with the
172 number of non-missing values, mean, standard deviation, median, and minimum/maximum
173 values. Qualitative variables will be expressed as a number and percentage of patients with
174 each qualitative characteristic. The missing values are not intended to be included in the
175 calculation of percentages. Sensitivity and specificity will be assessed specific to each method,
176 with respect to internal gold standard diagnostic work-up.

177

178 **V. RISKS AND BENEFITS**

179 *Potential Direct Benefits to Subject*

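### Section IV names only two-class accuracy measures, although the primary comparison is between many-category diagnoses that may also be unresolved

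*Protocol*

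**What the plan says.** Section IV states that "Sensitivity and specificity will be assessed specific to each method", and that this is done "with respect to internal gold standard diagnostic work-up". It says neither what counts as positive or negative nor how several entities are combined. For qualitative variables it otherwise promises counts and percentages, with missing values left out of the percentages.

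Other sections show what the methods return:

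- Section I.2 (Objectives): "To this end we generated a reference collection of 5,500 samples with the full spectrum of" hematological malignancies, each with a gold standard diagnosis by WHO classification.
- Section II.4 (Primary Study Endpoints): three algorithms are compared. The sequencing one is listed as "3) WGS and WTS sequencing plus matching to nearest digital sibling in 5,5k cohort". Algorithms (2) and (3) are first set against (1), the diagnosis at the referring site, and then against each other to see whether they reach a similar conclusion.
- Section I.1 (Background and Rationale): having no diagnosis is a real outcome of routine work-up, since "approximately 10 % of cases remain unresolved from a diagnostic point of view and hence do" not yield a satisfactory WHO diagnosis.
- Section II.2 (Duration of Study): "SIRIUS will be conducted for a total number of 110 patients with inconclusive diagnosis by" gold standard techniques.
- Section III.3 (Inclusion Criteria): the sample must contain at least 20% tumor. Section II.1 calls the design case-control, but no disease-free group is described.

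**The concern.** Sensitivity and specificity need a positive and a negative class. The question in Section II.4 is which entity each algorithm assigns and whether two algorithms assign the same one. That result has many categories, plus an unresolved category.

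Specificity is then the weak half of the pair. Depending on how the classes are formed, it either cannot be estimated or is high almost regardless of how often the entity is wrong. The study asks whether sequencing could replace current gold-standard methods. A specificity in the high nineties, quoted by itself, could be taken as support for replacement when it says little about agreement on the entity.

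**Working it through.** The protocol gives no expected sensitivity or specificity, so there is no stated figure to reproduce.

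**Inputs.** n = 110 (Sections II.2 and III.1). K, the number of entities, is not stated; I assume 10 to 30. e, the share of cases given a wrong entity, is an illustration: 0.3 and 0.5.

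**Reading A: malignancy yes/no.** All patients have a suspected or potential malignancy and at least 20% tumor content, and there is no disease-free group. Negatives are therefore few or absent, and specificity has almost no denominator. A case assigned to the wrong malignant entity counts as a true positive.

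**Reading B: one entity against the rest, pooled over entities.** Each case is a negative for K-1 entities, so there are n(K-1) negatives. Each wrong label adds one false positive, ne in all. Hence

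- pooled specificity = 1 - ne/[n(K-1)] = 1 - e/(K-1)
- pooled sensitivity = n(1-e)/n = 1 - e

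A case left without a diagnosis adds no false positive but lowers sensitivity.

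| K | Negatives, 110(K-1) | Specificity, 30% wrong entity | Specificity, 50% wrong entity | Specificity, 25% wrong entity and 25% unresolved |
|---|---|---|---|---|
| 10 | 990 | 1 - 33/990 = 96.7% | 1 - 55/990 = 94.4% | 1 - 27.5/990 = 97.2% |
| 20 | 2090 | 1 - 33/2090 = 98.4% | 1 - 55/2090 = 97.4% | 1 - 27.5/2090 = 98.7% |
| 30 | 3190 | 1 - 33/3190 = 99.0% | 1 - 55/3190 = 98.3% | 1 - 27.5/3190 = 99.1% |
| Pooled sensitivity | | 70% | 50% | 50% |

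At K=20, a 20-point difference in the share correctly classified (70% against 50%) moves specificity by 0.2/19 = 1.05 points. If every failure is an unresolved case, specificity is 100%.

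The pooled formula needs neither equal entity sizes nor evenly spread errors. A simulation with n = 110, unequal entity frequencies and 50% error gave mean specificities, averaged over entities, of 94.4% (K=10), 97.4% (K=20) and 98.3% (K=30), with sensitivity about 50%.

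**Single entities.** These can behave differently. With K=20 and equal sizes, an entity has 110/20 = 5.5 cases and 104.5 negatives. If all 55 errors fell on one entity, its specificity would be 1 - 55/104.5 = 47%, although the pooled figure stays at 97.4%. Entity-level sensitivity would be very imprecise: the exact 95% CI is 48% to 100% for 5/5 and 15% to 95% for 3/5.

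**The case against.** The strongest reply is that Section IV speaks of each method, not of each final diagnosis. Section II.4 lists component methods such as chromosomal banding and panel sequencing, and Section II.5 compares WES with WGS and counts missed actionable targets. Sensitivity and specificity could therefore mean detecting a lesion that the internal work-up reports, which is a proper two-class question. This stands: the reading is open, and the measures suit it. It still leaves the diagnosis comparison of Section II.4 with no fitting measure of its own.

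Second, the positive class and any averaging rule are commonly left to a statistical analysis plan, and none is shown here. Their absence alone is not the point. The point is that at entity level no pooling rule stops specificity from being near its ceiling.

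Third, the two measures come as a pair. A reader might infer that a method wrong half the time would pass unnoticed, or that the planned measures can show nothing about which method is better. The documents do not support that: pooled sensitivity would read 50% and expose the failure. Nor is 97% a figure of the protocol, since it depends on an assumed K.

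Fourth, Section IV already promises counts and percentages, and Section II.4 already describes a comparison of conclusions. This stands in part. The general sentence is not tied to agreement, disagreement or no diagnosis. Because it drops missing values, an unresolved case recorded as missing would leave the denominator.

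Fifth, scoring an entity as correct or wrong needs a reference, and the only one stated is the internal work-up, in patients whose diagnosis was inconclusive by gold standard techniques. This stands, and it limits the remedy to agreement between algorithms unless an independent reference exists.

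**Conclusion.** The point holds as one about fit. The only accuracy measures that Section IV names do not suit the diagnosis comparison that Section II.4 makes primary. At entity level, specificity is either nearly inestimable (malignancy yes/no) or about 94% to 98% when half of cases are misclassified (one-versus-rest, pooled, assuming K of 10 to 30). These figures are illustrations, and a single entity's specificity can be far lower if errors concentrate there.

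It does not follow that Section IV certainly intends entity-level scoring, that only these two readings exist, or that the pair of measures would hide a poor method. Sensitivity and specificity remain suitable for a defined binary finding. The change is worth making before analysis, because a better measure is available from the same data.

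**What to change.** In Section IV, make the main measure for the diagnosis comparisons a per-patient result over all 110 enrolled patients, in three categories: same WHO entity, different WHO entity, or no definitive diagnosis by one or both algorithms. Report it for (2) against (1), (3) against (1), and (2) against (3). Give each proportion with a 95% CI, keep unresolved cases in the denominator, and show the entity-by-entity cross-table of (2) against (3). With 110 patients, a proportion near 50% has a half-width of about 1.96 × √(0.5 × 0.5/110) = 9.3 points.

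Report correct against wrong entity only where a reference diagnosis independent of both algorithms is available. Restrict sensitivity and specificity to named two-class findings, such as detection of a defined lesion.

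The agreement measures use the planned data and cost a little more tabulation. The results will look less favorable than a specificity. Reporting correct against wrong would cost more wherever an independent reference diagnosis has to be obtained, but the main change does not depend on it.
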